4.1.3 Pathologic Criteria

Histologic confirmation of leukemia or myelodysplastic syndrome (MDS) at the time of diagnosis or recurrence

4.1.4 Specimen Samples

Sufficient leukemia or MDS specimen available for profiling from diagnosis or recurrence OR bone marrow aspirate or blood draw planned for clinical care anticipated to allow collection of minimum specimen for testing (See Sect.8.1 for description of specimen requirements); OR clinical tumor profiling using Rapid Heme Panel available in the medical record.

4.2 EXCLUSION CRITERIA

- #### 4.2.1
- Insufficient leukemia or MDS specimen available for profiling from recurrence or bone marrow evaluations NOT planned for clinical care; or peripheral blast percentage <20% AND clinical blood draw not planned; or patient sample did NOT already complete Rapid Heme Panel leukemia profiling clinically (See Sect. 8.1)

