8.0 BIOSPECIMEN COLLECTION AND PROCESSING

8.1 BIOSPECIMEN TYPES TO BE COLLECTED

8.1.1 Minimal Biospecimen Requirement

For patients with leukemia: The minimal requirements for enrollment are frozen mononuclear cells, DNA and RNA, or fresh bone marrow aspirate sample with at least 20% leukemia blasts in an EDTA tube collected from the most recent leukemia disease evaluation OR 3mL peripheral blood sample containing at least 20% blasts OR pheresis sample of at least 2 mL OR other fresh sample of patient leukemia cells in discussion with overall PI. The equivalent of 2 mL of liquid bone marrow aspirate is sufficient for RHP and fusion testing and is the minimal requirement for this study. Additional bone marrow/peripheral blood/DNA, etc, will be prioritized for profiling as detailed below. These requirements are not applicable if the patient has tumor profiling testing completed clinically using RHP.

For patients with MDS: The minimal requirements for enrollment are frozen mononuclear cells, DNA/RNA or fresh bone marrow aspirate sample in an EDTA tube collected from the most recent MDS disease evaluation. Blast percentage of 20% is not required for MDS samples. Additional bone marrow/peripheral blood/DNA, etc, will be prioritized for profiling as detailed below. These

requirements are not applicable if the patient has tumor profiling testing completed clinically using RHP.

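### Exclusion 4.2.1 joins its clauses with *or*, so as written it bars every patient without a prior clinical Rapid Heme Panel, and some with one, against 4.1.4 and 8.1.1

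*Combined protocol and SAP*

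**What the plan says.** Section 4.1.4 (inclusion) gives three routes joined by OR:

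- "Sufficient leukemia or MDS specimen available for profiling from diagnosis or recurrence";
- "bone marrow aspirate or blood draw planned for clinical care anticipated to allow collection of minimum specimen for testing";
- "OR clinical tumor profiling using Rapid Heme Panel available in the medical record".

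Section 4.2.1 (exclusion) has three clauses separated by semicolons and joined by *or*:

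- First clause: "Insufficient leukemia or MDS specimen available for profiling from recurrence or bone marrow evaluations NOT planned for clinical care".
- Second clause: "or peripheral blast percentage <20% AND clinical blood draw not planned".
- Last clause: "or patient sample did NOT already complete Rapid Heme Panel leukemia profiling clinically".

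Section 8.1.1 sets the minimum specimen for enrollment and then waives it: "These requirements are not applicable if the patient has tumor profiling testing completed clinically using RHP". For MDS it adds "Blast percentage of 20% is not required for MDS samples". Section 8.1.2 puts RHP first in the testing order for all patients. Section 9.1.2 has the study send samples for RHP and provides for a failed RHP in someone newly enrolled. Section 12.2 allows for 10% of enrolled patients being technical failures.

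**The concern.** An exclusion that mirrors *X or Y or Z* must read *not X and not Y and not Z*. Section 4.2.1 keeps the *or*, so a patient who qualifies by one route is excluded for lacking another. A site following the text exactly would enroll only patients whose leukemia had already been through a clinical RHP, although the study is set up to run that test itself.

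The criterion is in active use. Section 12.1 says new enrollment is to Cohort 1 only, across DF/CHCC and twelve named collaborating sites, and 5.5.1 has staff confirm eligibility on a checklist. The feasibility rule in 12.2 counts eligible Cohort 1 patients. Read literally, enrollees without a prior RHP are eligibility deviations. Read by intent, each site has to set the text aside.

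**Working it through.** **Inputs.** Five yes/no facts taken from 4.1.4 and 4.2.1: S, sufficient specimen; M, marrow planned; B, blood draw planned; H, peripheral blasts at least 20%; R, prior clinical RHP. They give 2^5 = 32 combinations. Two simplifications: a planned marrow is taken to yield the minimum specimen, and a planned blood draw does so only if H holds.

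**Inclusion 4.1.4** = S or M or (B and H) or R. It fails only when S, M and R are all no and B and H are not both yes, which is 3 combinations. So 32 − 3 = 29 satisfy it: 16 with R, and 16 − 3 = 13 without.

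**Exclusion 4.2.1.** The first clause can be parsed in two ways.

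- Plain *or*: (not S or not M) or (not H and not B) or not R. Escape requires S, M, R and at least one of H or B: 1 × 1 × 1 × 3 = 3 combinations.
- First clause meaning *neither*: (not S and not M) or (not H and not B) or not R. Escape requires R, at least one of S or M, and at least one of H or B: 1 × 3 × 3 = 9 combinations.

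| Combinations satisfying 4.1.4 | Excluded, plain *or* | Excluded, *neither* |
|---|---|---|
| Without prior RHP (13) | 13 | 13 |
| With prior RHP (16) | 16 − 3 = 13 | 16 − 9 = 7 |
| All (29) | 26 | 20 |

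If any planned blood draw counts under 4.1.4 whatever the blast percentage, 30 combinations satisfy it. The exclusions become 27 (14 of 14 without RHP, 13 of 16 with) and 21 (14 of 14, 7 of 16). The pattern is the same.

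**Cases excluded on both parses:**

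1. Sufficient specimen, marrow and blood draw planned, blasts at least 20%, no prior RHP: excluded by the last clause alone.
2. Prior RHP, no sufficient specimen, no marrow planned: excluded by the first clause, although 4.1.4 admits this patient and 8.1.1 waives the specimen minimum.
3. Prior RHP, sufficient specimen, marrow planned, but blasts under 20% and no blood draw planned: excluded by the second clause, which has no MDS exception.

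**Consistency with 12.2.** The plan's 13.5% reproduces as 0.90 × 0.15 = 0.135. If every enrollee already had a complete RHP and none failed, the same input would give 1.00 × 0.15 = 0.150. The 10% allowance therefore fits the 4.1.4 reading better than the literal 4.2.1.

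**Candidate repairs**, judged against the 29 combinations that satisfy 4.1.4 and the 3 that do not:

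- *And* after the semicolons only, first clause left as plain *or*: wrongly excludes 2 of 29 and misses 2 of the 3.
- *And* everywhere: wrongly excludes 0 and misses 2 of the 3.
- Exact complement of 4.1.4: excludes exactly the 3.

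**Specimen timepoint.** Section 4.2.1 speaks of recurrence, 4.1.4 of diagnosis or recurrence, and 8.1.1 and 9.1 of the most recent evaluation or marrow.

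**The case against.** The strongest reply is that this is a slip in a connective whose meaning nobody would mistake. Section 4.1.4 states the three routes plainly, 4.2.1 itself points to 8.1, and 8.1.2 and 9.1.2 have the study perform RHP. Read throughout as neither/nor, 4.2.1 excludes nobody whom 4.1.4 admits. The checklist that sites use is not among the documents, and 12.4.1 projects from previous enrollment, so recruitment has evidently gone ahead.

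Much of this stands. The intent is inferable and no harm is shown. The conflicts with 9.1.2 and 12.2 are by implication only: a patient with an RHP on file could be profiled again, and an older RHP does not guarantee success on the current sample. Section 12.4.1 also reports the rate among all enrolled Cohort 1 patients, so eligible patients are not the only stated denominator. The MDS point is supporting at most, because the sentence in 8.1.1 follows a list of MDS specimens that does not include blood. The combinations that a simple *and* would miss fail 4.1.4 anyway. The timepoint wording is secondary: only recurrence in 4.2.1 is plainly narrower than the rest.

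None of this removes the conflict with 4.1.4 and with the 8.1.1 waiver, which is direct. The neither/nor reading rescues the criterion only by replacing the connectives that are in it.

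**Conclusion.** The concern holds: 4.2.1 is wrong as written. Any grouping that keeps the final *or* excludes every patient without a prior clinical RHP (13 of 13 combinations that satisfy 4.1.4). It also excludes some patients with one (13 of 16 on the plain reading, 7 of 16 on the generous reading of the first clause). The supported word for the second group is *some*. The counts rest on the simplifications stated and weight every combination equally; the documents give no patient distribution, so they cannot be read as proportions of patients. The threshold of at least 8 of 100 is not affected. The correction should be made because this is an operative eligibility rule for the cohort still enrolling, but there is no evidence of wrongful exclusions.

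**What to change.** 1. Reword 4.2.1 as the complement of 4.1.4. For example: exclude only if all three hold: (i) no leukemia or MDS specimen that is sufficient under 8.1; (ii) no marrow aspirate or blood draw planned for clinical care from which the 8.1 minimum can be expected; (iii) no clinical RHP result on file. Changing only the *or* after each semicolon is not safe while the first clause can still be read as a plain *or*.
2. State the acceptable specimen timepoint once, in 8.1, and have 4.1.4, 4.2.1 and 9.1 refer to it. The sponsor must decide how the present wordings fit together.
3. Bring the eligibility checklist into line and confirm which wording it has applied so far.

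The cost is one reworded criterion, one clarified sentence and one checklist check. Sample size, endpoint, analysis and feasibility threshold do not change. If the checklist copied 4.2.1 literally, past screening decisions would need review; the documents do not say whether it did.

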5.0 SUBJECT ENROLLMENT

5.1 SUBJECT IDENTIFICATION

Potential subjects will be identified by the participant's treating physician during routine clinical care. In addition, potential subjects will also be identified through self-referral.

5.2 SUBJECT RECRUITMENT

Potential participants will be identified by their primary physician and referred to the study team at the appropriate participating institution for enrollment and education. In order to inform physicians about this project, the protocol will be presented at scientific and protocol conferences at the participating institutions in order to educate potential referring physicians of the protocol's existence. The protocol may be presented at scientific conferences and at grand rounds at regional institutions in order to educate potential referring physicians of the protocol's existence. The study will also be registered on clinicaltrials.gov. Patients who read this internet posting may self-refer. Self-referred patients will then be referred to the DFCI study team by their treating physician or through direct communication with the DFCI study team (contact information on clinicaltrials.gov). Remote consent will be conducted. If they are a patient at one of the participating institutions, they will be referred to the appropriate contact there for screening and enrollment. Otherwise, the protocol will not be advertised directly to patients and direct patient recruitment materials will not be created for this project.

5.3 ELIGIBILITY SCREENING

Eligibility screening will be conducted by qualified clinical research personnel. Every potentially eligible participant will be seen at one of the participating sites prior to enrollment unless the participant has self-referred or are referred by their physician and is not a patient at a participating institution. A complete assessment will be performed by qualified clinical research personnel to determine eligibility. This will be completed remotely by one of the participating sites if the patient is not a patient at one of those sites.

Screening will involve the following:

- Review of the participant's medical record
- If necessary, review of existing pathology slides documenting recurrent / refractory leukemia or MDS
- History and physical examination

Screening for referral participants will be the same above with the following modifications:

- The patient will not be required to have a history and physical exam at one of the participating sites. Review of the last clinical note of patient history and physical exam. The note needs to be dated within 90 days of screening.
- A full review of the eligibility documentation will be completed by an Investigator at one of the participating sites. That Investigator will be the enrolling physician for the participant.

5.4 SUBJECT CONSENT

The Principal Investigator, the Co-Investigators of this project, and/or the treating physician may offer eligible participants the opportunity to participate. Before issuing an invitation to participate, the Principal Investigator, the Co-Investigators, and/or the treating physician will provide a full explanation of this protocol to the potential subject and a parent or legal guardian (if subject less than 18), review the consent form with the potential subject and a parent or legal guardian (if subject less than 18), and answer any and all associated questions according to institutional and federal guidelines. Subjects and or their parents or legal guardian electing to participate in the study must sign the informed consent form following guidelines of the IRB at the enrolling Institution. At the DFCI and where local IRB guidelines do not specify, the procedures detailed in the remainder of this paragraph will be followed. Those subjects who elect to participate in the study must sign the informed consent form. For DFCI patients, Adobe Sign can be used as part of a remote consent process to sign the informed consent form for patients who are less than 10 years old or 18 years and older. For participants who are at an appropriate developmental age to provide assent, a parent or legal guardian must sign the consent form and the participant must assent to participation according to local institutional guidelines. For participants whose developmental age is not appropriate to provide assent, assent may be waived and a parent or legal

guardian must sign the consent form. Waiver of assent for participants whose developmental age is not appropriate for assent includes those patients who are of chronological age to assent but who have developmental delay or other neurologic condition. It should be determined by each investigator whether or not a waiver of consent is appropriate to the individual under consideration for entry onto the study.

Subjects who consent will be either given or mailed a signed copy of the form for their records. Subjects who request additional time to consider participation will be provided with a mailed or emailed copy of the consent form.

For potential participants who are not patients at a participating institution, Investigators and delegated staff who are genetic counselors who are trained and delegated to consent at trial study sites may consent the patient remotely via phone. Initially, the participant and/or their physician should express their interest in the study via email to one of the trial study sites after obtaining permission from the patient to do so. An intake questionnaire will then be sent to the patient in order to verify basic criteria of eligibility and provide a blank copy of the consent form and the patient-physician enrollment form (Appendix 18). Study staff may speak with, email, and/or send a letter to a physician directly for a patient who independently self-refers so that the primary physician listed on the intake form will be informed that their patient is interested in participating in this study (Appendix 22). Eligibility and availability and use of specimens for molecular profiling will be discussed. The primary physician will be asked to document their understanding of the project and agreement with receiving the MTT report if successful by completing the Physician section of the patient-physician enrollment form.

Once approval from the primary physician is confirmed, a time for a phone call consent discussion will be initiated with the participant. The consenting Investigator will initiate the consent discussion over the phone. Adobe Sign can be used as part of a remote consent process to sign the informed consent form for patients who are <10 years old or ≥ 18 years old. After the patient emails or mails the signed consent and fully completed patient-physician enrollment forms back to the enrolling study site, the patient will be assessed for eligibility as outlined above. If enrolled on the protocol, the patient will receive a letter of enrollment, a copy of the fully executed consent, and an enrollment specimen package if that is needed.

A participant's decision to participate or to not participate in this study will not affect the quality of care he or she receives.

5.4.1 Informed Consent Form

The informed consent forms will ensure that each participant/donor signatory understands and agrees to the following:

- The procurement of participant biospecimens through: (i) obtaining previously collected DNA and RNA extracted from a bone marrow sample; (ii) obtaining previously collected bone marrow samples where mononuclear cells have been frozen or DNA and RNA has been extracted and frozen; (iii) procedures that are called for by routine clinical care, after adequate material is collected for clinical diagnostic and treatment purposes.
- The use of biospecimens for tumor profiling with a targeted cancer gene panel, such as Rapid Heme Panel (RHP), and fusion testing in a CLIA lab when available and appropriate.
- The use of the tumor profiling information to match with a recommendation for a matched targeted therapy.

- The possibility that the recommendation may indicate a clinical course of action, or eligibility for a particular clinical trial. These profiling results and the treatment recommendation will be conveyed to them and their treating oncologist, who may not be a study investigator.
- The collection, storage and use of participant health information and linkage of participant health information with tumor profiling data by study staff at DFCI and BCH. This collection of data will be used for the purposes of creating a recommendation for a matched targeted therapy.
- The use of materials and clinical data for additional investigational tests and experiments some of which have not yet been designed. The clinical utility of such tests are unknown at this time and the results of these investigational tests will not be made available to participants or their physician(s). Some of the specific tests to be performed include whole genome sequencing, RNA sequencing, *in vitro* drug sensitivity testing and *in vivo* models. These additional investigations may be performed by researchers other than study investigators after approval of the study investigators. In this case, all specimens and data will be removed of identifying information.
- In some cases, specimens may be shared with for-profit companies that are working with researchers on a specific research project. Specimens will not be sold to any person or company for profit. Specimens shared with external companies will not contain identifying information. Subjects will not benefit from any financial gain to the institutions or their investigators based on these projects.
- Sharing or publication of de-identified genomic information in aggregate or individually. Subjects will be informed of the safeguards provided by de-identification but will also be informed that no one can predict how genomic information might be used in the future.
- There will be no costs to subjects for specimen contribution and no reimbursement to subjects for their participation.
- The optional activities for which consent is sought will be bundled into four individual requests for consent on the Consent Form: 1) return of germline result to the oncologist and this will prompt further testing; 2) willingness to complete questionnaires about perspectives on the matched targeted therapy study; 3) banking specimens for future use and investigational studies; 4) future contact by the study staff.
- Withdrawal of consent, as well as partial withdrawal from selected components, is possible at any time at participant discretion. Upon request by a participant, his or her specimens and derivative material will be removed from research specimen repositories. (Material collected for clinical purposes will not be removed from clinically relevant archives e.g., Departments of Pathology at individual institutions)
- Only study participants at sites participating in the survey portion of the study will be offered the opportunity to complete a questionnaire at the time of enrollment about their perspectives on genomic testing and asked to provide basic sociodemographic information including poverty measures. Participants who are not patients at participating sites will not be eligible for questionnaires. Those who complete this questionnaire will also be offered a follow-up questionnaire after the profiling results and interpretation are conveyed to the treating oncologist and again at the time of relapse/progression (if applicable). These questionnaires are optional and consent will be obtained for them. As of June 15, 2021, Questionnaire #1 is no longer being actively collected as part of this study. Questionnaires for timepoints 2 and 3 may be collected for patients who consented prior to this date, as is feasible for each site. Data from collected questionnaires continues to be analyzed by [name].

5.5 REGISTRATION AND WITHDRAWAL

All subjects, including those enrolled at collaborating sites and referred subjects, will be registered in the protocol registration database and assigned a study ID number in the Clinical Trials Management System (CTMS) Oncore. If collaborating sites require individual registration at institutional offices, the sites will be required to follow their own procedures as well as the central institution.

5.5.1 General Guidelines for DF/HCC Institutions

Institutions will register eligible participants in the CTMS OnCore.

A member of the study team will confirm eligibility criteria and complete the protocol-specific eligibility checklist.

5.5.2 Registration Process for DF/HCC Institutions

DF/HCC Standard Operating Procedure for Human Subject Research Titled *Subject Protocol Registration* (SOP #: REGIST-101) must be followed.

5.5.3 Registration Process for Participating Institutions

Eligible participants will be enrolled on study centrally at the DFCI by the Study Coordinator. Registration is only available during weekday business hours, between 9am-5pm EST. Once registration is confirmed, the DFCI study staff facilitating the registration will notify the participating site study staff regarding confirmation of registration. To register a participant, the following documents should be completed by the research nurse of data manager and faxed [REDACTED] or emailed to the Study Coordinator:

- Copy of pathology report confirming diagnosis
- Signed participant consent form
- HIPPA authorization form
- Eligibility Checklist

The coordinator will fax or email the participant study number to the participating site once the patient has been enrolled at DFCI.

